5.1 Design

In this experimental study, we will employ a three-arm design including (1) AI-alone, (2) Human-alone, (3) Human+AI to assess the accuracy of abstracting clinical elements from the patient chart. The accuracy of the abstraction will be compared against a pre-made “gold standard”. As detailed elsewhere, the study is powered for a direct comparison of the human alone vs human + AI arms as a non-inferiority analysis. For Arm 1, an autonomous AI algorithm (Mendel AI) will analyze patient medical records to extract relevant clinical elements (“AI-alone”). For Arm 2, a human researcher will manually review patient charts as per the current norm/practice (“Human-alone”). For Arm 3, a human researcher will utilize Mendel AI augmentation such that Mendel AI serves as a supportive tool in the decision-making process by providing the researcher a list of elements abstracted by the AI algorithm and a rank-order list of patients most likely to meet inclusion criteria for a trial (“Human+AI”). **For this study, we will**

only be using information from deidentified patient charts in Mendel's database. No Penn data will be utilized in this study.

We will employ 2 clinical research coordinators (CRCs) who will review and abstract specific clinical elements while reviewing the patient's electronic health record (EHR) which will include both "structured" (machine-readable) and "unstructured" (traditionally non-machine-readable; Mendel AI is uniquely capable of processing) data. To ensure no inter-rater differences in accuracy the CRCs will be assessed on a practice set of three charts and must meet an 80% threshold of agreement on review elements as well as concordance in chart-level accuracy as measured by Cohen's Kappa (threshold 0.6).

The components of the EHR that may be reviewed to abstract the data elements of interest may include:

- Physician Progress Notes
- Radiology Reports
- Pathology Reports
- Laboratory Reports
- Genetic/molecular sequencing and other genetic testing results
- Discharge Summaries
- Infusion Therapy reports

To help assess accuracy, the "Gold Standard" (to which all study arms will be compared) will be a manually annotated version based on review of at least 2 human abstractors (plus a tie-breaker if there is a discrepancy). This process will be led by the Mendel team, with independent oversight by the Penn research team to ensure consistency.

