First, the Mendel AI algorithm will review all patient charts, producing a machine-annotated version of each chart with AI-abstracted elements (AI-alone). Next, each CRC will review all patient charts. Each CRC will review half of their charts manually (Human-alone) and half of their charts using the machine-annotation and rank-order list (Human+AI). The order of review will be randomized such that manual reviews and AI-assisted reviews will be mixed, and such that each CRC will review half of the charts manually and half of the charts with AI assistance.

Secondary aim metrics (Efficiency) will be assessed by tracking the volume of completed prescreens per unit of time.

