8.2 Procedures

Our study will follow the design outlined above (section 5.1).

There is no informed consent needed for the use of this data. There will be no participant recruitment or compensation. Potential risks and benefits of the study are reported elsewhere (section 11.6).

Two CRCs will be hired to analyze de-identified patient data. CRCs will access the data via a password-protected portal, using a UPHS desktop and/or laptop. De-identified patient chart data will be included for analysis based on having a tumor type of interest. They will then review patient charts and record clinical elements of interest in the Mendel abstraction tool, which will be secured in a HIPAA-compliant external enclave. Summary-level data will be exported into datasheets for analysis. These datasheets will only be used and analyzed on UPHS equipment, or shared via HIPAA-compliant means.

Data will be analyzed using statistical software including Excel, R code, and STATA. For details of the analysis plan, see section 9.

Data elements that will be abstracted across all arms of the study include the following (the below list may change slightly pending further discussion among the research team):

Cancer Type and Staging

- Cancer Type
- Stage - Tumor
- Stage - Node
- Stage - Mets

Performance

- ECOG Performance Status

Prior Systemic Treatment

- Any Prior Platinum Therapy (e.g., Cisplatin, Carboplatin, Oxaliplatin)
- Any Other Prior Chemotherapy (e.g., 5-fluorouracil, Leucovorin, Capecitabine, Irinotecan, Pemetrexed, Paclitaxel, Docetaxel, Gemcitabine)
- Any Prior Immunotherapy (e.g., Atezolizumab, Nivolumab, Pembrolizumab)

Biomarkers for CRC

- KRAS
- MSI-H
- MSS
- BRAF
- HER2
- NTRK
- DPYD

Biomarkers for NSCLC

- EGFR
- ALK
- ROS1
- KRAS
- BRAF
- NTRK
- cMET
- RET
- PDL1

Others

- Outcomes (remission, residual disease, recurrence, loco-regional recurrence, distant recurrence)
- Responses (complete response, stable disease, partial response, mixed response, disease progression)

9. Analysis plan

The primary study will be powered on a retrospective paired, non-inferiority design to evaluate abstraction accuracy of elements commonly used to help screen patients for clinical trials. The two arms are (1) human reviewers versus (2) human reviewers utilizing predictions from Mendel AI. The primary outcome, the percentage of gold standard items correctly abstracted, will be measured for each chart. Noninferiority can be established by comparing the difference in the

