mean proportion correct between the human-augmented and Human-alone arms with a predefined non-inferiority margin, Δ .

The one-sided hypotheses to test noninferiority of average chart-level accuracy of a Human+AI abstraction approach, compared with a Human-alone approach are outlined below:

$$H_0: \mu_{h-ai} - \mu_h \leq -\Delta \text{ (Null hypothesis)}$$

$$H_a: \mu_{h-ai} - \mu_h > -\Delta \text{ (Alternative hypothesis)}$$

Test statistic:

$$T_n = \frac{(\mu_{h-ai} - \mu_h) + \Delta}{\sqrt{\frac{Var(D)}{n}}}$$

Sample size equation for a noninferiority, paired study design:

$$n = \frac{(z_{1-\beta} + z_{1-\alpha})^2 \sigma^2}{((\mu_{h-ai} - \mu_h) + \Delta)^2} = \frac{(z_{1-\beta} + z_{1-\alpha})^2 \sigma^2}{(D + \Delta)^2}$$

As a secondary analysis, we will test the superiority of the Human+AI arm for achieving greater average chart-level accuracy, compared with the Human-alone arm. Our hypotheses are:

$$H_0: \mu_{h-ai} \leq \mu_h \text{ (Null hypothesis)}$$

$$H_a: \mu_{h-ai} > \mu_h \text{ (Alternative hypothesis)}$$

Sample size equation for a superiority, paired study design:

$$n = \frac{(z_{1-\beta} + z_{1-\alpha})^2 Var(D)}{(\mu_{h-ai} - \mu_h)^2}$$

Parameter	Description
μ_{h-ai}	Mean proportion of criteria correctly abstracted by AI-augmented human reviewers
μ_h	Mean proportion of criteria correctly abstracted by Human-alone reviewers
$D = \mu_{h-ai} - \mu_h$	Mean difference in chart-level accuracy between arms
Δ	Non-inferiority margin, set as 0.05 for conservative sample size estimates.
$z_{1-\beta}$	Critical value at $1-\beta$, where $1-\beta$ represents the desired power and β represents Type II error

$Z_{1-\alpha}$	Critical value at $1-\alpha$, where α = Type I error
σ^2	$n^* \text{Var}(D)$, where n is the sample size and $\text{Var}(D)$ is the variance of the mean difference in chart-level accuracy

*Note: μ_{h-ai} , μ_h , $\Delta > 0$.

From our initial calculations, 400 individual patients will achieve an estimated statistical power greater than 90% for this non-inferiority study with a Type I error of 5%. This was determined from simulations for different realistic parameter scenarios for TNR, event rate, and concordance assumptions showing that the needed sample size rarely exceeded 400.

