The goals of the secondary analyses are to compare the efficiency of screening among the three study arms. We will analyze efficiency, defined by comparing the average number of minutes per chart review, measured for each chart. A nonparametric, paired Wilcoxon Rank Sum test with continuity correction will compare overall median efficiency of chart abstraction between arms.

The following are post-hoc analyses to be conducted after the pre-specified main analyses. Superiority of chart-level accuracy for the Human+AI arm relative to Human-alone will be tested using a one-sided paired t-test with an unspecified inferiority margin. A sensitivity analysis will repeat the primary chart-level accuracy outcome analysis with a less strict definition of an accurate match to the gold standard set. To assess whether there is a difference in accuracy among the 12 trial eligibility criteria, criterion-level accuracy will be compared assessed between arms. To assess criterion-level accuracy, a two-sided, paired t-test will be conducted with Bonferroni correction for multiple hypotheses (i.e., $\alpha = 0.05 / n$, where $n=12$ was the number of criteria studied). For any criterion with a statistically significant difference in mean criterion-level accuracy, superiority of the Human+AI arm for criterion-level abstraction will be then assessed with an additional one-sided hypothesis with an unspecified superiority margin. Lastly, we repeat both the chart-level accuracy analysis and efficiency analyses while stratifying by chart characteristics that include chart complexity, length, order, and cancer type.

Descriptive statistics, including means, medians, proportions, and ranges, will be used to summarize each analyses. All statistical analyses will be conducted using appropriate statistical software, and will rely on a predetermined significance level (e.g., $\alpha = 0.05$). Effect sizes and confidence intervals will be reported where applicable to provide further context to the findings.

10. Investigators

[name], PhD (Principal Investigator) is [name] and [name] University Professor in Health Policy and Medical Ethics and Co-Director of the Healthcare Transformation Institute.

[name], MPP (Sub-Investigator) is Assistant Professor of Health Policy and Medicine and Innovation Faculty at the Penn Center for Cancer Care Innovation (PC3I).

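### Neither the accuracy test nor the time test uses which coordinator had AI on each chart; with balanced halves this costs precision only, and the remedy is nearly free

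*Combined protocol and SAP*

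**What the plan says.** Section 5.1 employs two coordinators. On coverage it says "Next, each CRC will review all patient charts", and on the split, "Each CRC will review half of their charts manually (Human-alone) and half of their charts using the machine-annotation and rank-order list (Human+AI"). It does not say that the two coordinators' halves are complementary.

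Section 9 states "The primary study will be powered on a retrospective paired, non-inferiority design". The primary statistic compares the "mean proportion correct between the human-augmented and Human-alone arms with a predefined non-inferiority margin", and its denominator is the variance of the paired difference over n, with no term for coordinator. For time, "A nonparametric, paired Wilcoxon Rank Sum test with continuity correction will compare overall median efficiency of chart abstraction between arms". The test is named as a rank-sum but described as paired, so I read it as the signed-rank test. The analyses to be repeated by subgroup involve "stratifying by chart characteristics that include chart complexity, length, order, and cancer type"; coordinator is not listed.

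The one safeguard is in Section 5.1: "To ensure no inter-rater differences in accuracy the CRCs will be assessed on a practice set of three charts", and they "must meet an 80% threshold of agreement on review elements as well as concordance in chart-level accuracy", the latter with a kappa threshold of 0.6. It concerns accuracy. Nothing comparable covers speed.

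**The concern.** A chart can contribute to a paired analysis only if it has one manual and one AI-assisted review. As each coordinator reads each chart, those two reviews come from different coordinators. A within-chart difference therefore carries the AI effect plus the coordinator gap on about half the charts, and the AI effect minus the gap on the rest.

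The planned tests treat this alternating gap as random noise, although the design records exactly where it falls. At stake is the width of the accuracy interval and, more plausibly, the power of the time comparison, where two people may differ in pace and no qualification check applies. With only two coordinators, readers will also ask whether the result depends on who had the AI, and the plan has no analysis that answers this.

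**Working it through.** **Inputs from the plan.** n = 400 charts, margin 0.05, one-sided 5%, stated power above 90% (Section 9). The plan gives no SD of the paired difference, no expected difference, no coordinator gap and no expected time saving. These are assumed below and shown as ranges.

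**The plan's own figure.** The 400 cannot be reproduced without an SD, but it can be back-solved. With a true difference of 0, n = (1.282 + 1.645)² σ² / 0.05² = 400 gives σ = 0.342. So 400 charts give at least 90% power for any SD up to 0.342.

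**Model.** For chart i, difference = AI effect + a·g + error. Here a is +1 or −1 according to who used AI, g is the coordinator gap, and s is the SD within an allocation group. With a fixed 200:200 split, g cancels from the mean, whose true standard error is s/√400. The planned standard error is √(s² + g²)/√400, too large by √(1 + g²/s²).

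**Accuracy.** Power with the planned test is Φ[(D + 0.05)·√400/s − 1.645·√(1 + g²/s²)]. Setting g = 0 inside the root gives the adjusted test.

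| True difference 0 | Adjusted | Planned, gap 10 points | Interval wider by |
|---|---|---|---|
| s = 0.20 | 99.96% | 99.92% | 12% |
| s = 0.25 | 99.1% | 98.7% | 8% |
| s = 0.342 | 90.0% | 88.7% | 4% |

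The largest loss over all s at D = 0 is 0.36 points for a 5-point gap (s = 0.406) and 1.43 for a 10-point gap (s = 0.403). If Human+AI were truly 2 points worse, the maxima would be 0.99 and 4.01. For scale, independent binomial errors on 12 items at 60% to 90% accuracy (an assumption) give s = √(2p(1−p)/12), that is 0.20 down to 0.12.

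A simulation at s = 0.342 with an extreme gap of 20 points agrees with the formula: planned power 84.8% against 84.6% by formula, and type I error 2.4% planned against 4.4% adjusted.

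**Minutes.** Assumed: lognormal times, log-SD 0.4 to 0.8 between charts and 0.25 to 0.50 residual, 200 charts per allocation group, raw minutes, continuity correction, 3,000 runs per cell. The comparator is a rank-sum test of coordinator 2 minus coordinator 1 minutes between the two groups. The gap is common to both groups and cancels, while the AI effect enters with opposite signs. Power (%) at a 1.5-fold speed gap, two-sided 5%, planned then adjusted:

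| Chart SD, residual SD | 8% gain | 10% gain | 15% gain |
|---|---|---|---|
| 0.6, 0.35 | 65.9, 82.2 | 88.2, 94.8 | 99.9, 100 |
| 0.6, 0.25 | 82.1, 96.7 | 97.6, 99.8 | 100, 100 |
| 0.6, 0.50 | 44.5, 54.9 | 66.2, 73.9 | 97.3, 98.5 |
| 0.4, 0.35 | 69.7, 85.8 | 90.3, 96.5 | 100, 100 |
| 0.8, 0.35 | 62.5, 78.2 | 87.4, 94.0 | 99.9, 100 |

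Crossing the full range of SDs, not only these five pairs, gives losses of about 8 to 18 points at an 8% gain (about 4 to 10 one-sided), roughly 0 to 10 at 10%, at most about 2 at 15%, and none at 25%. For a 1.2-fold gap the loss is about 0 to 4 points at gains of 8% or more.

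With no AI effect and SDs of 0.6 and 0.35 (12,000 runs), the planned test rejects 1.3% of the time at a 1.5-fold gap; the adjusted test rejects 5.1%.

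**The case against.** The strongest reply is that nothing in the conclusions is wrong. Each coordinator works half manually and half with AI in mixed order, which already balances the gap between arms. What remains inflates the variance and makes the tests cautious. That stands.

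The accuracy effect is also slight. The 1.4-point figure is a maximum that needs an SD near 0.40, where power is already below the stated 90% with no gap at all. The sample-size simulations varied concordance assumptions whose content is not shown, so reviewer disagreement may already be allowed for in the 400. This stands too.

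For minutes, the aim is secondary with no stated power, the speed hypothesis in Section 2 is directional, and Section 11.6.2 anticipates large time savings, at which the loss disappears. The larger losses need both a wide speed gap and a modest gain, and the plan indicates neither.

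A reader might infer more: that the AI effect is confounded with coordinator, or that a non-inferiority claim would be unsafe. The documents do not support that, because with balanced complementary halves the gap cancels and the tests are conservative. A reader might also fear bias if lost charts unbalance the split. The charts are existing records and no attrition mechanism is described, so I place no weight on this.

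What survives is that the practice check does not settle the matter. Eighty per cent agreement on three charts leaves room for an accuracy gap of up to 20 points, and speed is not checked.

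**Conclusion.** The point holds as an efficiency refinement, not as a validity flaw. The planned tests discard information that the design generates, and the cost is precision alone. For the primary accuracy decision the cost is small under any plausible SD. For minutes it ranges from nothing to a material loss of power, depending on the coordinators' relative speed and the AI gain.

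Two assumptions carry this. Complementary halves are inferred from the pairing; if some charts received two manual or two AI-assisted reviews, the pairing itself would fail and this model would not apply. All magnitudes are conditional on assumed SDs, gaps and gains, and the time figures also on lognormal times. Confidence in the mechanism is high; confidence that the loss will matter in practice is moderate at best.

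**What to change.** In Section 9, for accuracy: estimate the mean difference as the average of the two allocation-group mean differences (coordinator 1 AI-assisted; coordinator 2 AI-assisted), with its standard error from the pooled within-group variance on n − 2 degrees of freedom. With equal groups the estimate is identical to the planned one.

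In Section 9, for minutes: prespecify one test. For each chart take coordinator 2 minus coordinator 1 minutes, and compare the two allocation groups with a Wilcoxon rank-sum test.

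In Section 5.1: state that the two coordinators' halves are complementary, so that every chart has one manual and one AI-assisted review.

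In Section 8.2: keep coordinator identity for each chart in the exported file, since only export of summary-level data is mentioned there.

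The cost is one degree of freedom for accuracy, one replaced test for minutes and one retained column. No charts or reviews are added.

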5.2 Study duration

We anticipate the "review" phase of this study where human researchers are abstracting data from patient charts to take roughly 6 months, followed by 6 months for analysis.

5.3 Target population

This study will include de-identified patient charts from Mendel's databases from patients in community oncology practices with a diagnosis of non-small cell lung cancer (NSCLC) or colorectal cancer (CRC) with a minimum of 5 patient documents and data within 5 years from the time of data extraction. No Penn data will be utilized in this study and we will use standard EHR datasets.

5.4 Accrual

Mendel AI upholds a database of clinical data for deidentified patients from participating community-based oncology practices. This data will be utilized for this study. As noted above, no Penn data will be utilized in this study.

5.5 Key inclusion criteria

A patient chart will be included for analysis based on the following three screening criteria:

- A diagnosis of NSCLC or colorectal cancer
- A minimum of 5 patient documents in the Mendel database
- Most recent document was within 5 years from the time of data extraction

6. Subject recruitment

No subjects will be involved with this work.

7. Subject compensation

There will be no compensation for the use of subjects' de-identified data collected as part of routine clinical care.

8. Study procedures

8.1 Consent

The data utilized for analysis will be obtained from existing electronic health records (EHR) that have already been collected as part of routine clinical care and collated in the Mendel AI datasets. As such, patients will not be directly involved in the research process, and the study will not require any new data collection or intervention from patients.

Most importantly, all patient data used in the study has been de-identified and anonymized to ensure the protection of patient privacy and confidentiality.

In light of these considerations, patients will not need to provide consent for their data to be included in the study. This approach aligns with the ethical standards for retrospective studies using de-identified data, and the study design has been developed to ensure compliance with relevant regulations and guidelines on patient privacy and data protection.

As noted before, no Penn data will be utilized in this study.

8.2 Procedures

Our study will follow the design outlined above (section 5.1).

There is no informed consent needed for the use of this data. There will be no participant recruitment or compensation. Potential risks and benefits of the study are reported elsewhere (section 11.6).

Two CRCs will be hired to analyze de-identified patient data. CRCs will access the data via a password-protected portal, using a UPHS desktop and/or laptop. De-identified patient chart data will be included for analysis based on having a tumor type of interest. They will then review patient charts and record clinical elements of interest in the Mendel abstraction tool, which will be secured in a HIPAA-compliant external enclave. Summary-level data will be exported into datasheets for analysis. These datasheets will only be used and analyzed on UPHS equipment, or shared via HIPAA-compliant means.

Data will be analyzed using statistical software including Excel, R code, and STATA. For details of the analysis plan, see section 9.

Data elements that will be abstracted across all arms of the study include the following (the below list may change slightly pending further discussion among the research team):

Cancer Type and Staging

- Cancer Type
- Stage - Tumor
- Stage - Node
- Stage - Mets

Performance

- ECOG Performance Status

Prior Systemic Treatment

- Any Prior Platinum Therapy (e.g., Cisplatin, Carboplatin, Oxaliplatin)
- Any Other Prior Chemotherapy (e.g., 5-fluorouracil, Leucovorin, Capecitabine, Irinotecan, Pemetrexed, Paclitaxel, Docetaxel, Gemcitabine)
- Any Prior Immunotherapy (e.g., Atezolizumab, Nivolumab, Pembrolizumab)

Biomarkers for CRC

- KRAS
- MSI-H
- MSS
- BRAF
- HER2
- NTRK
- DPYD

Biomarkers for NSCLC

- EGFR
- ALK
- ROS1
- KRAS
- BRAF
- NTRK
- cMET
- RET
- PDL1

Others

- Outcomes (remission, residual disease, recurrence, loco-regional recurrence, distant recurrence)
- Responses (complete response, stable disease, partial response, mixed response, disease progression)

9. Analysis plan

The primary study will be powered on a retrospective paired, non-inferiority design to evaluate abstraction accuracy of elements commonly used to help screen patients for clinical trials. The two arms are (1) human reviewers versus (2) human reviewers utilizing predictions from Mendel AI. The primary outcome, the percentage of gold standard items correctly abstracted, will be measured for each chart. Noninferiority can be established by comparing the difference in the

mean proportion correct between the human-augmented and Human-alone arms with a predefined non-inferiority margin, Δ .

The one-sided hypotheses to test noninferiority of average chart-level accuracy of a Human+AI abstraction approach, compared with a Human-alone approach are outlined below:

$$H_0: \mu_{h-ai} - \mu_h \leq -\Delta \text{ (Null hypothesis)}$$

$$H_a: \mu_{h-ai} - \mu_h > -\Delta \text{ (Alternative hypothesis)}$$

Test statistic:

$$T_n = \frac{(\mu_{h-ai} - \mu_h) + \Delta}{\sqrt{\frac{Var(D)}{n}}}$$

Sample size equation for a noninferiority, paired study design:

$$n = \frac{(z_{1-\beta} + z_{1-\alpha})^2 \sigma^2}{((\mu_{h-ai} - \mu_h) + \Delta)^2} = \frac{(z_{1-\beta} + z_{1-\alpha})^2 \sigma^2}{(D + \Delta)^2}$$

As a secondary analysis, we will test the superiority of the Human+AI arm for achieving greater average chart-level accuracy, compared with the Human-alone arm. Our hypotheses are:

$$H_0: \mu_{h-ai} \leq \mu_h \text{ (Null hypothesis)}$$

$$H_a: \mu_{h-ai} > \mu_h \text{ (Alternative hypothesis)}$$

Sample size equation for a superiority, paired study design:

$$n = \frac{(z_{1-\beta} + z_{1-\alpha})^2 Var(D)}{(\mu_{h-ai} - \mu_h)^2}$$

Parameter	Description
μ_{h-ai}	Mean proportion of criteria correctly abstracted by AI-augmented human reviewers
μ_h	Mean proportion of criteria correctly abstracted by Human-alone reviewers
$D = \mu_{h-ai} - \mu_h$	Mean difference in chart-level accuracy between arms
Δ	Non-inferiority margin, set as 0.05 for conservative sample size estimates.
$z_{1-\beta}$	Critical value at $1-\beta$, where $1-\beta$ represents the desired power and β represents Type II error

$Z_{1-\alpha}$	Critical value at $1-\alpha$, where α = Type I error
σ^2	$n^* \text{Var}(D)$, where n is the sample size and $\text{Var}(D)$ is the variance of the mean difference in chart-level accuracy

*Note: μ_{h-ai} , μ_h , $\Delta > 0$.

From our initial calculations, 400 individual patients will achieve an estimated statistical power greater than 90% for this non-inferiority study with a Type I error of 5%. This was determined from simulations for different realistic parameter scenarios for TNR, event rate, and concordance assumptions showing that the needed sample size rarely exceeded 400.

The goals of the secondary analyses are to compare the efficiency of screening among the three study arms. We will analyze efficiency, defined by comparing the average number of minutes per chart review, measured for each chart. A nonparametric, paired Wilcoxon Rank Sum test with continuity correction will compare overall median efficiency of chart abstraction between arms.

The following are post-hoc analyses to be conducted after the pre-specified main analyses. Superiority of chart-level accuracy for the Human+AI arm relative to Human-alone will be tested using a one-sided paired t-test with an unspecified inferiority margin. A sensitivity analysis will repeat the primary chart-level accuracy outcome analysis with a less strict definition of an accurate match to the gold standard set. To assess whether there is a difference in accuracy among the 12 trial eligibility criteria, criterion-level accuracy will be compared assessed between arms. To assess criterion-level accuracy, a two-sided, paired t-test will be conducted with Bonferroni correction for multiple hypotheses (i.e., $\alpha = 0.05 / n$, where $n=12$ was the number of criteria studied). For any criterion with a statistically significant difference in mean criterion-level accuracy, superiority of the Human+AI arm for criterion-level abstraction will be then assessed with an additional one-sided hypothesis with an unspecified superiority margin. Lastly, we repeat both the chart-level accuracy analysis and efficiency analyses while stratifying by chart characteristics that include chart complexity, length, order, and cancer type.

Descriptive statistics, including means, medians, proportions, and ranges, will be used to summarize each analyses. All statistical analyses will be conducted using appropriate statistical software, and will rely on a predetermined significance level (e.g., $\alpha = 0.05$). Effect sizes and confidence intervals will be reported where applicable to provide further context to the findings.

10. Investigators

[name], PhD (Principal Investigator) is [name] and [name] University Professor in Health Policy and Medical Ethics and Co-Director of the Healthcare Transformation Institute.

[name], MPP (Sub-Investigator) is Assistant Professor of Health Policy and Medicine and Innovation Faculty at the Penn Center for Cancer Care Innovation (PC3I).

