The objective of this study is to assess and compare the accuracy and efficiency of three different approaches to abstracting clinical data used to identify oncology patients who meet the inclusion criteria for participation in clinical trials. The three approaches under evaluation include: (1) an autonomous AI algorithm (Mendel AI; developed by artificial intelligence startup company Mendel) which analyzes patient medical records to extract relevant clinical facts (“AI-alone”); (2) a human researcher who manually reviews patient charts as per the current norm/practice (“Human-alone”); and (3) a human researcher utilizing AI augmentation (“Human+AI”), where Mendel AI serves as a supportive tool in the decision-making process by providing the researcher a list of elements abstracted by the AI algorithm and a rank-order list of patients most likely to meet inclusion criteria for a trial.

The study primarily aims to compare (1) the chart-level accuracy of the Human+AI collaboration relative to Human-alone given the relevance of this comparison for real-world clinical workflows, defined by the percentage of pre-identified chart elements classified correctly compared against a predetermined “gold standard”; and (2) the efficiency of the Human+AI vs. Human-alone arms, defined by the time per chart review in minutes, measured for each chart.

Our hypotheses are (1) the Human+AI arm will be non-inferior in accuracy when compared to the Human-alone arm, in relation to a predetermined “gold standard”, and (2) that a Human+AI arm will be superior in speed of abstraction when compared to Human-alone screening.

The identification of eligible patients for clinical trials is a critical component of clinical research, as it directly impacts patient recruitment, study enrollment, and the generalizability of research findings. Currently, the process of identifying eligible patients often relies on manual chart review by clinical research staff, which can be time-consuming, labor-intensive, and prone

to human error. Consequently, eligible patients may be overlooked, and opportunities for trial participation may be missed. The integration of AI technology into the patient identification process has the potential to enhance the accuracy and efficiency of this critical task, leading to improved clinical trial recruitment and outcomes.

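### Does the primary accuracy score rest on two different units, the listed chart elements and the 12 criteria?

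*Combined protocol and SAP*

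**What the plan says.** Section 2 (Overall objectives) gives the definition: chart-level accuracy is "defined by the percentage of pre-identified chart elements classified correctly compared against a predetermined" gold standard.

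Section 8.2 supplies the list, introduced by "Data elements that will be abstracted across all arms of the study include the following", with the caveat that "the below list may change slightly pending further discussion among the research team".

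Section 9 opens by saying that the study is to "evaluate abstraction accuracy of elements commonly used to help screen patients for clinical trials", and then states: "The primary outcome, the percentage of gold standard items correctly abstracted, will be measured for each chart". Its parameter table describes the Human+AI mean as "Mean proportion of criteria correctly abstracted by AI-augmented human reviewers", with matching wording for Human-alone, and describes D as a difference in chart-level accuracy.

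The post-hoc paragraph of Section 9 introduces a separate analysis of criterion-level accuracy: "To assess whether there is a difference in accuracy among the 12 trial eligibility criteria". The Bonferroni divisor there is 12, which "was the number of criteria studied".

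No section maps the elements to the 12 criteria.

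**The concern.** One score carries three names: elements, items and criteria. The third stands in the table that defines the means being tested, and the only count given for criteria is 12. Neither cancer's list has 12 entries.

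The chart score is a simple proportion, so whatever is counted is weighted equally. Counted by element, a panel of seven or nine biomarkers is a large part of the score; counted once per panel, it is a small part. The same abstraction errors could then meet the 0.05 margin under one reading and miss it under the other. If the unit were open when results came in, the primary conclusion could depend on a choice made afterwards.

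**Working it through.** **1. The plan's own figure.** Section 9 gives 400 patients, power above 90%, one-sided Type I error 5% and margin 0.05. It states neither the SD of the paired difference nor the expected D, so 400 cannot be reproduced. Solving the plan's formula backwards at D = 0 gives SD = 0.05 × √400 / (1.282 + 1.645) = 1.00 / 2.927 = 0.342. The sample size holds for any SD up to that value, whichever unit is used.

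**2. Counts from Section 8.2.** Shared elements: 4 (type and stage) + 1 (ECOG) + 3 (prior treatment) + 2 (others) = 10. Colorectal: 10 + 7 = 17. Lung: 10 + 9 = 19. Counting each biomarker panel once gives 10 + 2 = 12 overall and 11 applicable to any one chart. That grouping is an inference; the plan does not state it.

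**3. Loss that reaches the margin.** Take an equal loss of L points on each of the ten shared elements and no change on biomarkers. With K equally weighted units the score falls by 10L/K, so 5 points is reached at L = 5K/10.

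| Unit | K | L at the margin | Fall in score when L = 7 |
|---|---|---|---|
| Element, colorectal | 17 | 8.5 | 4.12 |
| Element, lung | 19 | 9.5 | 3.68 |
| 12 criteria | 12 | 6.0 | 5.83 |
| 11 criteria per chart | 11 | 5.5 | 6.36 |

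The point differences fall on opposite sides of the margin strictly between 6.0 and 8.5 for colorectal charts if the denominator is 12. The lower limit becomes 5.5 only with 11.

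**4. Dependence on the grouping.** If s of the 12 criteria are shared ones, each with loss L, the limit is 5 × 12/s: 6.67 for s = 9, 7.5 for s = 8, 8.57 for s = 7. The last exceeds 8.5, so no window remains for an all-colorectal sample.

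**5. From point difference to test result.** P(declare non-inferiority) = Φ((D + 0.05)/(SD/20) − 1.645), with n = 400 and an assumed SD of 0.15 to 0.30.

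| Loss on shared elements | Colorectal, by element | Lung, by element | 12 criteria |
|---|---|---|---|
| 6 points | 0.62 to 0.25 | 0.79 to 0.34 | 0.05 |
| 7 points | 0.32 to 0.14 | 0.54 to 0.22 | 0.003 to 0.014 |
| 8 points | 0.11 to 0.07 | 0.28 to 0.13 | 0.003 or less |

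If elements are instead assumed independent, with Human-alone accuracy 85 to 95%, the colorectal figures by element are 0.74 to 0.96 at 6 points, 0.39 to 0.65 at 7 and 0.12 to 0.16 at 8. In the upper part of the window a colorectal sample usually fails under both units.

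**6. The opposite pattern.** Put the loss on the biomarkers alone. By element the margin is reached at 5 × 17/7 = 12.1 points per marker (colorectal) or 5 × 19/9 = 10.6 (lung). With 11 criteria and the panel scored as an average it takes 5 × 11/1 = 55 points. Here the element score is the stricter one. Another panel rule would give another figure, and the plan states none.

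**7. Following the defined term.** Section 2 attaches chart-level accuracy to elements. The hypotheses in Section 9 concern average chart-level accuracy, and the table's row for D uses that term again. The post-hoc paragraph gives criterion-level accuracy its own name, and 12 appears only there. A second unit for the primary score arises only by joining one word in the table to a count in a different, post-hoc analysis.

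**The case for a change.** The strongest case for acting is that the parameter table is where the tested means are defined, and it says criteria. The word recurs soon afterwards with a closed count of 12, while the Section 8.2 list is left open. A reader cannot prove that criteria means elements. In a lung sample with a 6-point loss on the shared elements, the chance of declaring non-inferiority would be 0.34 to 0.79 by element against 0.05 with 12 criteria. A unit with that much influence should not be selectable after the data are seen.

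Part of this stands. The wording varies, the mapping is absent, and for some patterns of error the choice would matter. But the Section 2 definition is in the plan in advance, so scoring the primary outcome on 12 grouped criteria would be a visible departure from it. If the list was in fact settled at 12, as Section 8.2 leaves room for, elements and criteria would coincide and there would again be one unit. The large contrast also needs a particular pattern: an equal loss on all ten shared elements, none on biomarkers, a sample of one cancer, and a grouping that keeps all ten as separate criteria. The plan enrols both cancers.

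The plan also leaves the strict match and the scoring of blanks unstated. These are further scoring details to be written down, and they do not show that either unit is wrong.

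**Conclusion.** The concern does not call for a change. The documents support one coherent reading: the chart score is the share of applicable listed elements that agree with the gold standard, *criteria* in the parameter table is loose wording, and 12 is the number of tests in the post-hoc criterion-level analysis. An analyst working from Section 2 would score it that way.

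If the other reading were meant, the two would disagree on the point difference for shared-element losses of about 6 to 8.5 points (colorectal) or 6 to 9.5 (lung). This assumes 12 equally weighted criteria that include all ten shared elements, and unchanged biomarker accuracy. The lower limit moves with the grouping, and the window can close. It is not true that the choice of unit decides the test result throughout that range.

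Nor do the documents show either unit to be wrong. Weighting by element gives biomarkers 7/17 = 41% or 9/19 = 47% of the score. Counting each panel once, with 11 units per chart, gives the shared elements 10/11 = 91%. Each is stricter for some errors and more lenient for others, which is a fair trade-off. What is missing is a mapping and consistent vocabulary; the primary test, its margin and the sample size are unaffected. Confidence is moderate, because the reading rests on how the terms are used, with no explicit statement that elements and criteria are the same.
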